EXCLUSION CRITERIA	
EXCLUSION CRITERIA:
 
1. Previous history of infection in the affected joint.2. Active local or systemic infection that may affect the prosthetic joint.3. Insufficient bone stock on femoral or tibial surfaces.4. Skeletal immaturity.5. Neuropathic arthropathy.6. Osteoporosis or any loss of musculature or neuromuscular disease that compromises the affected limb.7. A stable, painless arthrodesis in a satisfactory functional position.8. Severe instability secondary to the absence of collateral ligament integrity.9. Rheumatoid arthritis accompanied by an ulcer of the skin or a history of recurrent breakdown of the skin.10. Patient has previously received partial or total knee arthroplasty for the ipsilateral knee.11. Patient is currently participating in any other surgical intervention studies or pain management studies.12. Patient is known to be pregnant or considered a member of a protected population (e.g., prisoner, mentally incompetent, etc.).13. Patient has a known or suspected sensitivity or allergy to one or more of the implant materials.
STATISTICAL REPORTING	Clinical performance will be evaluated for radiographic success, pain and function, and implant survival by summarizing the data descriptively. Categorical data (e.g., gender, component size) will be reported using frequency and percentages with 95% Confidence Interval (CI) over the time periods of interest. Continuous data (e.g. age, weight) will be summarized using mean, standard deviation, minimum, median, maximum, and 95% CI over the time periods of interest. Implant survival will be summarized using a Kaplan-Meier method and presented with rates (expressed as percentages) and CI. Routine summaries of complication data will be in the form of frequencies and percentages.

This protocol is written based on guidelines from ISO 14155:2011 Standard for Clinical Investigation of Medical Devices For Human Subjects – Good Clinical Practice [1] and is in accordance with US Code of Federal Regulations 21 CFR Parts 11, 50 and 56 [2].

III. Data Collection Overview

The following tables indicate required forms and activities to be completed at the given time point:

Form Name	Preop	Surgical to Immediate Postop	6 Weeks Postop (± 2 weeks)	6 Months Postop (± 1 month)	1 Year Postop (± 1 month)	2 Years Postop (± 2 months)
Site and Subject completed:						
Informed Consent Form	X●					
Site completed:						
Inclusion/Exclusion Criteria	X					

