Performance of the commercially available *NexGen TM Monoblock Tibia* and *NexGen TM Modular Tibia* used in primary cementless tibia total knee arthroplasty will be evaluated for radiographic parameters, pain and function, and survival of the device. Data collected in this study will be summarized descriptively and descriptive summaries will be the basis of any study reports issued. These summaries may be used for interim study reports and may also be used to support regulatory submissions, presentations, and/or publications. Additional surgical technique and instrumentation data may be collected and evaluated.

A. General Statistical Methods

Statistical methodology will consist of summarizing collected data descriptively. Categorical data (e.g., gender or race) will be summarized using counts and percentages, and 95% Confidence Interval (CI), over the time periods of interest. Continuous data, such as age, will be summarized by using means, medians, standard deviation, minimum, maximum, and 95% CI over the time periods of interest. Implant survival and return to function will be summarized using a Kaplan-Meier method and presented with rates (as percentages) and confidence intervals.

B. Sample Size

A minimum of 132 subjects are to be enrolled in this study, with approximate equal distribution of at least 66 *NexGen TM Monoblock* and 66 *NexGen TM Modular* subjects. The *NexGen TM Monoblock Tibia* and *NexGen TM Modular Tibia* are considered 2 single-arms being analyzed separately. Sample size is based upon 6 to 10 sites enrolling between 22 to 30 subjects per site.

Based on *NexGen*'s expected success rate of 98% at two years on the primary endpoint and using a 10% non-inferiority margin against a 98% performance goal, 57 subjects are required to achieve 80% power to test non-inferiority. 57 subjects also allow the Sponsor to control the Type-1 alpha error at 0.05. Assuming a 12% loss to follow-up over 2 years, approximately 66 subjects need to be enrolled for each single arm.

XIII. References

- [1] ISO 14155:2011(E). Clinical investigation of medical devices for human subjects – Good clinical practice.
- [2] US Food and Drug Administration. eCFR – Electronic Code of Federal Regulations Title 21. Retrieved April 25, 2017, from https://www.ecfr.gov/cgi-bin/text-idx?SID=e0cb187b56d9cb0279bb080f88b8121d&mc=true&tpl=/ecfrbrowse/Title21/21tab_02.pl.

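### Section XII.B claims power and Type-1 error control for a non-inferiority test, but the analysis sections plan only descriptive summaries and state no decision rule, sidedness or interval method for the primary endpoint

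*Combined protocol and SAP*

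**What the plan says.** Section XII.B sizes each of the two separately analysed arms for a test. It assumes a 98% two-year success rate on the primary endpoint, "using a 10% non-inferiority margin against a 98% performance goal". It then says that "57 subjects are required to achieve 80% power to test non-inferiority" and that "57 subjects also allow the Sponsor to control the Type-1 alpha error at 0.05". Enrolment follows from attrition: "Assuming a 12% loss to follow-up over 2 years, approximately 66 subjects need to be enrolled for each single arm".

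The analysis text plans no test:
- Section XII: "descriptive summaries will be the basis of any study reports issued". The same paragraph says the summaries "may also be used to support regulatory submissions, presentations, and/or publications".
- Section XII.A: "Statistical methodology will consist of summarizing collected data descriptively". For categorical data this means counts, percentages and a 95% confidence interval, with gender and race as the examples. No interval method is named.
- Synopsis, Statistical Reporting: "Clinical performance will be evaluated for radiographic success, pain and function, and implant survival by summarizing the data descriptively". Radiographic success is the domain of the primary endpoint.

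The endpoint statements in the synopsis and Section VI describe the absence of progressive tibial radiolucencies at two years. They attach no hypothesis or success threshold to it.

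**The concern.** Power and Type-1 error are properties of a decision rule. Section XII.B claims both, but the analysis sections contain no rule to which they could belong. Followed literally, XII.A produces a percentage with an interval and stops there; no test is carried out.

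What is at stake is whether a non-inferiority statement may be attached to each arm's result, and on what basis. As the text stands, a report with no verdict follows XII and XII.A, while a claim of powered non-inferiority could cite XII.B. Someone making that claim would have to choose the interval method and the sidedness, possibly after seeing the data. This matters more because the plan allows the summaries to support regulatory submissions.

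**Working it through.** **Inputs, all from XII.B.** Expected rate p1 = 0.98; goal 0.98; margin 0.10, read as absolute, so the implied null rate is p0 = 0.98 − 0.10 = 0.88; power 0.80; alpha 0.05, sidedness not stated; 12% loss; 66 enrolled per arm. The value 88% is not written in the plan; it is the subtraction of two figures that are.

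**Step 1: reproduce the 57.** One-sample normal approximation with null and alternative variances:

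n = [(z_a·√(p0(1−p0)) + z_b·√(p1(1−p1))) / (p1−p0)]²

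- One-sided 0.025: [(1.960·√(0.88·0.12) + 0.8416·√(0.98·0.02)) / 0.10]² = [(0.6369 + 0.1178)/0.10]² = 56.96, rounded up to 57.
- One-sided 0.05: [(0.5345 + 0.1178)/0.10]² = 42.55, rounded up to 43.

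So 57 matches one-sided 0.025 (two-sided 0.05) with an absolute margin. A relative margin (p0 = 0.98 × 0.90 = 0.882) would give 58.59. For enrolment, 57/0.88 = 64.8, consistent with approximately 66.

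**Step 2: read the planned 95% interval as the test.** Suppose non-inferiority is concluded when the two-sided 95% lower limit exceeds 88%. At 57 evaluable, 55 successes give:
- exact (Clopper-Pearson): 87.9%, fails;
- score (Wilson): 88.1%, passes.

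The exact rule therefore needs at least 56/57, and the score rule at least 55/57.

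**Step 3: operating characteristics at 57, from the binomial distribution.**

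| Rule | Power, true rate 98% | One-sided error, true rate 88% |
|---|---|---|
| Exact 95% CI (≥56/57) | 0.3161 + 0.3678 = 68.4% | 0.0007 + 0.0053 = 0.6% |
| Score 95% CI (≥55/57) | 68.4% + 21.0% = 89.4% | 0.6% + 2.0% = 2.6% |

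An exact one-sided 0.05 test also needs at least 55/57, so it too has 89.4% power and 2.6% error.

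**Step 4: neighbouring numbers of evaluable subjects.** Exact and score rules allow the same number of failures at every n from 45 to 69 except 57. At 56 both need 55 successes (power 69.1%). At 58 both need 56 (power 89.0%).

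**Step 5: average over loss.** Assume each of 66 subjects is lost independently with probability 0.12, so that the evaluable number is Binomial(66, 0.88) with mean 58.1. Mean power is then 80.8% (exact) or 83.6% (score).

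**The case against.** The best counter-argument is that the passages can be read together. The primary endpoint is categorical, XII.A plans a 95% interval for categorical data, and XII.B supplies the goal and margin. Comparing the lower limit with 88% is a non-inferiority test, and two-sided 95% is the level that reproduces 57. On this view only a linking sentence is missing. The reading is reasonable, but no section states it. XII.A presents the interval as part of a descriptive summary and says the methodology consists of such summaries. Even if the reading is accepted, the method is unnamed, and at the plan's own n that decides whether 55/57 passes.

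Three other parts of the objection stand. The rate and a given interval are the same whether or not a verdict is attached, so a reader who inferred that the plan yields two incompatible reports would go too far. Exact and score rules differ at only one n between 45 and 69. The drop in power just below 58 comes from attrition and the discreteness of the binomial, and it would remain after the text is reconciled.

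A reader might also infer that the sample size is wrong, or that Type-1 error is seriously inflated. The documents support neither. The 57 reproduces, and a score interval at 57 meets both stated figures. A materially inflated error would require an interval method that no section names.

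**Conclusion.** The concern holds in this form: the stated power and Type-1 control belong to no analysis that the plan describes. The claim in XII.B is therefore wrong as written, although 57 and 66 are not shown to be wrong as numbers. If the 95% interval is meant as the test, power at 57 is 68.4% or 89.4% and one-sided error 0.6% or 2.6%, depending on whether the interval is exact or score. The number of subjects alone does not control the error; the rule does.

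These figures assume an absolute margin, a true rate of 98% for power and 88% for error, and independent subjects. The averaged powers also assume independent 12% loss from 66. The inconsistency itself rests on the text and needs none of these assumptions. It should be fixed before analysis. It is a matter of specification, not a fatal fault in a post-market, uncontrolled study.

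**What to change.** Choose one of two before analysis.

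**1. If the test is intended.** Amend the descriptive-only sentences in XII, XII.A and the synopsis so that they except the primary endpoint; adding a rule without this would leave the conflict in place. Then add: *For each arm, non-inferiority is concluded if the lower limit of the two-sided 95% score CI for the 2-year primary success rate exceeds 88% (98% minus 10 percentage points).* In XII.B, state that alpha is one-sided 0.025 (nominal) and that power is 69% at 56, 89% at 57 and 89% at 58 evaluable, and about 84% averaged over an assumed independent 12% loss from 66.
- If an exact interval is named instead, the sentence that 57 subjects achieve 80% power must be replaced: power is 68% at 57 and 89% at 58, and about 81% averaged over the same loss.
- If one-sided 0.05 is intended, say so; an exact test then has 89% power at 57.

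**2. If description only is intended.** Delete the power and Type-1 error sentences in XII.B and justify 57 by precision. For example, 56 successes in 57 give an exact 95% CI of 90.6% to 99.96%.

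**Cost.** Option 1 means edits in XII, XII.A and the synopsis, one new sentence for the rule, and a rewritten power statement in XII.B. Option 2 replaces two sentences in XII.B. Enrolment of 66 per arm and all study procedures are unchanged under both.
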